*The following drugs are strong inhibitors of CYP3A4: ketoconazole, itraconazole, clarithromycin, ritonavir, indinavir/ritonavir, lopinavir/ritonavir, and conivaptan.⁴⁸

Randomization:

A consecutive sample of subjects that meet eligibility requirements and give informed consent will be randomized to two study groups via a randomization number generated from a random numbers table. Based on their randomization number patients will be given a prescription (for either tamsulosin or a likeappearing placebo) from the Mayo pharmacy at least one week prior to the date of surgery. The pharmacy will record which group the patient has been assigned to in a central pharmacy database. This database will then be used in the perioperative and postoperative period to maintain the patient's drug designation and administration while in the hospital. The randomization will be blinded to both the treating physician's team and the patient until the end of the study and data analysis is undertaken.

Drug Administration:

In order to achieve full steady state concentrations of the drug by the time of surgery, patients will be instructed to take the assigned drug for 5 days prior to surgery, as well as the morning of surgery. Thus, patients will be given 6 pills of the study medication or the like-appearing placebo at a preoperative clinic visit. On the morning of surgery patients will be admitted to Saint Marys Hospital as morning admissions and proceed to surgery that day based on the surgical schedule. Data on medication compliance will be collected and recorded at that time. Patients will continue taking tamsulosin 0.4mg or like-appearing placebo provided by the Mayo Pharmacy beginning on post-operative day one and continuing every day during their postoperative hospital course until the time of discharge. At that time the primary treating team will write an order to discontinue the study medication. Because each patient will be at therapeutic steady state concentrations of the drug by the time of surgery, shorter hospital stays should not underestimate the potential treatment benefit of this medication. Standard postoperative orders for patients undergoing decompressive cervical or lumbar laminectomy and/or spinal fusion have been in place for neurosurgical patients and will continue to be used during this study (postoperative order set

MC1156-404). The cost of the study medication will be covered by the study and patients will not be charged.

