Pre-operative Post Void Residual Urine Volume:

A pre-operative post void residual (PVR) volume of urine will be obtained on all enrolled patients at their pre-operative clinic visit prior to beginning their drug assignment (tamsulosin or placebo). This will be measured using the same technique as will be performed during the post-operative period (see Outcome Measures below). This baseline PVR will help determine efficacy of the study drug as outcomes are measured. The residual will be done by a member of the study staff and patients will not be charged.

Outcome Measures:

The primary outcome measure will be the incidence of POUR. POUR will be defined as any of the following:

- 1) Estimated post-void residual (PVR) volume of urine greater than or equal to 300 mL.
- 2) Estimated retention urine volume of greater than or equal to 500 mL in patients unable to void.
- 3) Patients experiencing discomfort or distension and unable to void with lesser residual urine volume than 500 ml

Neurosurgical nursing staff currently follow the institutional Urinary Retention Protocol (MC1156-214rev0610.) This protocol includes an algorithm for both diagnosing postoperative urinary retention and its treatment. This protocol has been in use for all postoperative spine patients since 2003 and the most current version is based on the above definition of urinary retention. All residual volume of urine measurements will be made with a standard bladder scanner instrument that is currently in use on the neurosurgery wards. Presence or absence of urinary retention will be recorded in the electronic medical record (EMR) for later data retrieval and analysis.

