Secondary outcome variables include duration of POUR among those patients in which it occurs, number of intermittent catheterizations in those with urinary retention, incidence of UTI, and duration of hospital stay. Measurement of the duration of POUR will closely coincide with the methods for recording incidence of POUR as discussed above. The decision to use and the time of removal of indwelling urinary catheters will be left to the discretion of the primary neurosurgical team. Time of indwelling catheter removal after surgery will serve as time zero for beginning calculation of postoperative urinary retention duration if the patient later requires in and out straight catheterization. For patients without an indwelling catheter, the time patients leave the operating room will serve as time zero. Per the Urinary Retention Protocol (MC1156-214rev0610),

patients found to be experiencing POUR will be ordered to have a straight in and out catheterization performed by a member of the catheterization team after failure of noninvasive measures (e.g. trigger techniques, bladder massage, application of warmth, relaxed environment, privacy, ambulation) by the attending nursing staff member. Urinary retention will be considered resolved after two consecutive post-void residual urine scans have demonstrated less than 300 ml residual urine volume in a patient spontaneously voiding. The number of intermittent catheterizations is recorded in the EMR in accordance with the standardized protocol.

Patients suspicious of having a UTI based on signs and symptoms of urinary frequency, urgency, burning or pain will have a urine sample (via catheterization or spontaneous void) sent for routine urinalysis, gram stain, and culture/sensitivity by the nursing staff member responsible for the patient or the primary neurosurgical team, per instructions documented on the Urinary Retention Protocol (MC1156-214rev0610). Positive UTIs will be defined as positive gram stain in the presence of signs or symptoms of UTI, urine white blood cell count elevation, and positive culture of >10⁴ cfu/ml. Patients will be treated with the appropriate antibiotic based on culture sensitivity.

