Length of hospital stay will be recorded for all patients following the surgical procedure with the day after surgery defined as postoperative day one. The medical record will be reviewed following discharge to determine if hospital discharge date was dependent on POUR or other reason (e.g. uncontrollable pain, mobility requiring physical therapy or inpatient rehabilitation, or other medical complications delaying discharge).

In addition to the primary and secondary outcome measures, baseline characteristics will be collected on all patients via the medical record including age, height and weight, past history of postoperative urinary retention or diagnosis of benign prostatic hyperplasia (not on treatment), length and type of surgery, estimated blood loss during surgery, total intravenous fluids administered perioperatively, time to oral analgesic use (in hours), total analgesic use during the postoperative period, time to first postoperative mobility (in hours), and any adverse events thought to be related to administration of the study medication. These variables will be used as baseline comparisons between the two groups to ensure homogeny and be used in statistical adjustment if differences between the groups are significant after randomization.

Unanticipated events:

There is the potential for patients to experience urinary retention as outpatients after inpatient urinary retention has resolved. This is quite unusual to occur after urinary retention has resolved as defined above and may indicate the patient needs further investigation by a urologic surgeon. Patients will be counseled by nursing staff prior to dismissal regarding the signs and symptoms of urinary retention and directed to seek medical attention with appropriate urology referral should the treating physician deem this is appropriate.

Patients experiencing prolonged postoperative urinary retention (> 5 days) will be seen by the urology consult service for recommendations regarding further investigation and treatment. The study group designation may be broken at this point to determine which group the patient is in regarding treatment medication if deemed necessary by the urology consult service to guide further treatment.

Patients experiencing severe adverse events such as profound hypotension, arrhythmia, or allergic reaction will be evaluated by the primary neurosurgical team with appropriate intervention or consultation as deemed necessary.

Quality Control:

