All statistical analysis and report of results will be done in a confidential manner and no information linking individual patients with data from the study will be shared outside of the study. Every effort will be made to keep this data anonymous once it has been collected.

Analysis of the Data:

Baseline characteristics will be compared between the two study groups using a chi-squared or Fisher's Exact Test for categorical variables and multiple two sample t-tests for continuous variables. The primary outcome variable, incidence of POUR, as well as other categorical variables, such as incidence of UTI, will be analyzed using a chi-squared test or Fisher's Exact Test. Duration of POUR will be compared using a two sample non-paired t-test comparing means. An appropriate nonparametric test (e.g. Wilcoxon Rank Sum) will be used for non-normal appearing data as can be anticipated for length of hospital stay. Differences in the groups with respect to baseline variables will be used to construct a multiple linear regression model to control for potential confounding factors if necessary. Intention to treat analysis will be used for all comparisons between groups.

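### Variables measured after dosing, including drug-related adverse events, are treated as baseline and adjusted for when they differ; the plan does not say the unadjusted test still decides

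*Combined protocol and SAP*

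**What the plan says.** The last part of Outcome Measures introduces a list of baseline characteristics. Some belong there: age, height, weight, history of retention or untreated BPH, type of surgery. The list continues with length of surgery, blood loss, perioperative fluids, time to oral analgesic and total analgesic use, and ends with "time to first postoperative mobility (in hours), and any adverse events thought to be related to administration of the study medication". The whole list serves to compare the arms and will "be used in statistical adjustment if differences between the groups are significant after randomization". No significance level is given for that trigger.

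Under Drug Administration, "patients will be instructed to take the assigned drug for 5 days prior to surgery, as well as the morning of surgery". All seven later items therefore follow both randomisation and first dose.

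Analysis of the Data assigns the primary outcome a simple comparison: POUR incidence, "as well as other categorical variables, such as incidence of UTI, will be analyzed using a chi-squared test" or Fisher's exact test. It then says that group differences in baseline variables "will be used to construct a multiple linear regression model to control for potential confounding factors if necessary", and closes with "Intention to treat analysis will be used for all comparisons between groups".

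One true baseline measure, the pre-dose residual volume, is absent from the list. Its own section says "This baseline PVR will help determine efficacy of the study drug as outcomes are measured", without a method.

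**The concern.** A covariate is safe to adjust for when neither the drug nor the outcome can change it. The seven later items do not meet that condition, and an adverse event attributed to study drug cannot be a baseline characteristic. The significance trigger makes this worse, because a variable the drug has shifted is the one most likely to be selected.

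The documents themselves suggest routes. Background names perioperative fluid and postoperative analgesia as risk factors for POUR. Adverse Events gives orthostatic hypotension as the main drug risk, which could alter fluids. The retention protocol starts with "noninvasive measures (e.g. trigger techniques, bladder massage, application of warmth, relaxed environment, privacy, ambulation", so time to first mobility may respond to POUR itself.

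Adjusting for such a variable removes part of the treatment effect or adds a spurious one, and departs from the promised intention-to-treat comparison. If the adjusted and unadjusted results disagree, the plan has no rule for which one counts.

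**Working it through.** **1. The plan's own figure.** Analysis of the Data gives 20% v 10%, one-sided α 0.05, power 0.80 and 175 per arm. Without continuity correction, n = [1.645·√(2·0.15·0.85) + 0.842·√(0.16 + 0.09)]² / 0.10² = 156.6, so 157. With the correction it is 177, within two of the stated 175; the two-sided version gives exactly the stated 219. The trial is therefore sized on an unadjusted test. Power of that test at 175 per arm, uncorrected, is Φ[(0.10 − 1.645·√(0.255/175)) / √(0.25/175)] = Φ(0.98) = 0.84.

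**2. Assumptions.** The documents give no drug effect on any of the seven variables, so the shifts and associations below are assumed. The trigger is taken as a two-sided t-test at 0.05. When it fires, the adjusted result decides; otherwise the unadjusted test does.

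**3. How often the trigger fires.** For a shift of d SD, the test statistic centres on d·√(175/2) = 9.35d.
- d = 0.1: 0.94, fires in about 15% of trials
- d = 0.2: 1.87, about 46-47%
- d = 0.3: 2.81, about 80%

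**4. Direction and size of the bias.** To first order, adjusted difference = total difference − (change in POUR risk per SD) × d. The change per SD is roughly p(1−p)·ln(OR). With average p(1−p) = (0.16 + 0.09)/2 = 0.125 and d = 0.3:
- OR 1.5: 0.125 × 0.405 × 0.3 = 1.5 points; × 0.80 firing = 1.2 points
- OR 2.0: 0.125 × 0.693 × 0.3 = 2.6 points; × 0.80 = 2.1 points

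A true 10-point benefit should thus average about 8-9 points if the drug lowers the covariate and about 11-12 if it raises it.

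**5. Simulation, fluids** (175 per arm; 6,000 trials per null cell, 4,000 per effect cell; entries are OR 1.5 / OR 2.0).

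| Shift (SD) | Rejection, zero net effect | Power, 20% v 10% | Mean benefit (points) |
|---|---|---|---|
| −0.3 | 2.1% / 1.0% | 73.5% / 66.8% | 8.7 / 7.7 |
| 0 | 5.0% / 4.4% | | |
| +0.1 | 6.0% / 5.6% | | |
| +0.2 | 7.3% / 9.3% | | |
| +0.3 | 10.2% / 16.0% | 91.2% / 94.6% | 11.4 / 12.2 |
| +0.5 | 17.4% / 32.9% | | |

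Unadjusted rejection was 4.7-5.3% in every null cell, and unadjusted power about 84%. At ±0.1 SD power moves by about 1-2 points. Linear and logistic adjustment agreed within 0.2 percentage points.

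**6. Drug with no effect on POUR that moves a correlated variable.** Here the covariate does not cause POUR but shares an unmeasured cause with it, and the drug shifts it by 0.4 against an SD of √2 (0.28 SD). In 10,000 trials the trigger fired in 75%. Rejection was 14.6% when the drug raised the covariate and 1.3% when it lowered it, against 4.7% unadjusted.

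**7. POUR changes time to mobility** (SD 12 h, true 20% v 10%, 10,000 trials). A change of 12 h per case gives an arm difference of 0.10 × 12 = 1.2 h on an SD of √(144 + 144 × 0.125) = 12.7 h, or 0.094 SD. For 24 h it is 2.4/14.7 = 0.163 SD.
- 12 h: trigger fires in 14%, mean benefit 9.6 points, power 82% against 84%
- 24 h: trigger fires in 34%, mean benefit 8.1 points, power 74% against 84%

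**8. Control case.** For a covariate that the drug does not move, the triggered procedure rejected in 4.9-5.0% of 20,000 null trials. The trigger alone, on true baseline variables, does not inflate type I error; nor does choosing a linear over a logistic model.

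**The case against.** The strongest reply is that the primary analysis is already clear. One test is named for POUR, the sample size rests on it, and the regression sentence follows the continuous outcomes, names a linear model and is qualified as needed only if necessary. On that reading the adjusted model is supplementary, and every figure for a switched decision assumes something the plan never states. This is the natural reading, and it is why the problem is limited. It does not settle the matter: Outcome Measures says without exception that the listed variables will be used in adjustment, and no sentence gives precedence.

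Second, zero net effect in the fluids table is not an inert drug. It requires a direct benefit that cancels the harm done through fluids: at +0.3 SD, a direct odds ratio of exp(−0.3·ln 1.5) = 0.89 or exp(−0.3·ln 2) = 0.81. That is correct, and the 17-33% at +0.5 SD must not be read as the chance of declaring an inert drug effective. Step 6 needs no such cancellation, though it still needs the drug to move the covariate.

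Third, the plausible shift may be small. The one related figure is orthostatic hypotension in 0.2%, or 0.35 patients per 175, and nothing supports 0.3-0.5 SD. The mobility route is also thin: ambulation is one of several examples, all patients are ambulated with nursing help under the ward protocol, and no text says POUR changes time to first mobility. Both points limit the likely size.

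Finally, surgery duration, fluids and analgesia are cited risk factors. That justifies recording them, not adjusting for them once dosing has begun.

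**Conclusion.** The concern holds. The adjustment rule is wrong as written: it calls variables measured after dosing baseline and adjusts for them when they differ, which conflicts with the intention-to-treat comparison. The resulting bias can run either way. Its size cannot be read from the documents. It is negligible if the drug moves none of these variables and POUR does not alter them, small at 0.1 SD, and material at 0.3 SD if the adjusted result is allowed to decide. The named chi-squared or Fisher test is sound and unaffected. The defect should be fixed; it does not invalidate the design, and the planned 175 per arm is unchanged.

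**What to change.** In Analysis of the Data, state that the unadjusted chi-squared or Fisher test by assigned arm decides the primary hypothesis. Delete the significance trigger from Outcome Measures and the matching conditional sentence from the analysis section.

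Add one supportive adjusted analysis of POUR, run whatever the observed imbalance, in a model suited to a binary outcome: logistic regression with the marginal risk difference reported. Fix a short list of pre-treatment covariates, for example pre-dose residual volume, age, sex, history of POUR or BPH, planned region (cervical or lumbar) and planned procedure (laminectomy or fusion). The planning rates imply 175 × (0.20 + 0.10) = 52.5 events, or 7.5 per term for these six plus treatment, so the list should not be longer. This also gives the pre-dose residual volume a defined use. A linear model with the same covariates can stay for continuous outcomes.

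Report the intra- and post-operative variables and adverse events by arm as outcomes, never as covariates.

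The cost is a few sentences, with no added patients, visits or procedures: residual volume is already measured in every patient before dosing, and the other covariates are in the record. Any power gain from the supportive model is a bonus that depends on assumed covariate strength: about 85%, 86% and 88% at AUC 0.61, 0.68 and 0.76, against 84-85% unadjusted.

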The use of an uroselective Alpha-1-antagonist to reduce the incidence and duration of postoperative urinary retention following spine surgery

NCT01568918

February 01, 2012

Title:

The Use of a Uroselective Alpha-1-Adrenergic Receptor Antagonist to Reduce the Incidence of Postoperative Urinary Retention Following Spine Surgery

Investigators:

[name]., [name]., [name], R.N., [name] (Statistician), [name] (Office of Research and Regulatory Support), [name], [name]., [name]. (Research Mentor), [name].

Abstract:

Postoperative urinary retention (POUR) occurs in up to 38% of neurosurgical patients undergoing simple decompressive spine procedures, with even higher rates estimated after complex spinal procedures such as instrumented fusion. This can result in multiple intermittent catheterizations for bladder decompression, increased incidences of urinary tract infection, and prolonged hospital stays. Previous non-neurosurgical series using nonspecific alpha-1adrenergic receptor antagonists have had some success in both the prevention and treatment of POUR. However, according to a recent Cochrane review, the use of alpha-blockers for the prevention and treatment of POUR is underresearched and there remains a need for well-designed clinical trials evaluating these drugs. The current neurosurgical practice at Mayo Clinic has both the clinical volume and infrastructure to support a randomized controlled trial evaluating the use of tamsulosin, a uroselective alpha-1-adrenergic receptor antagonist, for the prevention and treatment of POUR. If successful, this could not only result in decreased incidence and duration of POUR, but also in decreased hospital stays with an associated significant reduction in healthcare costs.

Background:

Postoperative urinary retention (POUR) is a common problem following neurosurgical procedures, specifically spine surgery. Estimates of incidence of POUR range from 2 to 69% in various surgical series depending on the type of surgery, anesthetic technique, and the method used to evaluate urinary retention.¹⁻⁸ In the only neurosurgical series specifically addressing the incidence of POUR, it was found to occur in 38% of patients undergoing simple decompressive spine surgeries with nearly an equal distribution between men

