Study subjects will be recruited through referral for surgical consultation in the neurosurgery outpatient clinic at Mayo Clinic Rochester. Individual surgeons will determine whether a surgery is indicated in particular patients. After the decision has been made to proceed with surgery, the patient will be interviewed for eligibility into the study, consented, and enrolled by the respective neurosurgeon's physician extender (R.N. or N.P.). Eligibility criteria are included in Table 1 and will be reviewed with each patient during the preoperative visit addressing the eligibility requirements for entry into the study. Patients undergoing simple spinal procedures (discectomy and foraminotomy procedures) that typically have next day hospital discharges and low incidences of POUR will be excluded from the study. It is not anticipated that subject retention will present a major challenge because the duration of study follow up is limited to the duration of the postoperative hospital stay. It is estimated that subjects will be actively participating in the study for approximately 8-12 days in most cases. Subject recruitment will continue until at least 175 subjects have been recruited into both the treatment and control groups and have completed the study. An interim analysis will be performed with unblinded data from the research pharmacy when 75 or more patients have completed participation.

Inclusion Criteria	Exclusion Criteria
≥ 35 years (Males & Females)	< 35 years
Cervical Laminectomy Cervical Posterior Fusion Cervical Anterior/Posterior Fusion	Cervical Anterior Discectomy and Fusion Cervical Anterior Corpectomy Cervical Posterior Discectomy Cervical Foraminotomy
Lumbar Laminectomy Lumbar Posterolateral Fusion Lumbar Interbody Fusion	Lumbar Discectomy (METRx or Open) Lumbar Foraminotomy Lumbar Anterior Fusion
	Myelopathy with bladder dysfunction
	Patients currently taking an alpha- antagonist [#]
	Patients with history of allergy or sensitivity to tamsulosin or other alpha-antagonist
	History of prostatectomy or urologic surgery involving the bladder or urethra
	Severe liver disease or end-stage renal disease

Table 1:

	Patients taking strong inhibitors of CYP3A4*
	Mental disability or prisoner

[#]The following drugs are alpha antagonists: alfuzosin, doxazosin, prazosin, terazosin, tamsulosin, and phenoxybenzamine.^{46,47}

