The primary outcome measure of incidence of POUR was used to calculate sample size. Data gathered from multiple series suggests that postoperative urinary retention occurs in 2-69% of patients undergoing a variety of surgical procedures, with 38% occurring in neurosurgical patients undergoing simple decompressive spinal procedures. Using 20% (P2=0.20) as a conservative estimate of incidence, an effect size of 10% for the primary outcome variable (P1=0.10) would be clinically meaningful. Thus, P2-P1 = 0.10. Because incidence of urinary retention is a binary categorical variable, a chi-squared test can be used to compare groups. Based on a type I error rate of 0.05 (α), a type II error rate of 0.20 (β), and power of 0.80 the estimated sample sizes needed for each group are as follows. For a one sided type 1 error, there would need to be 175 subjects in each group. For a two-sided type 1 error there would need to be 219 subjects in each group. A one-sided test of significance is reasonable in this study because an increase in incidence of POUR experienced in the tamsulosin treated group is not anticipated and would not add additional useful information in terms of using tamsulosin for POUR. Thus, a reasonable estimate for sample size is 175 subjects in both the treatment and control groups. Furthermore, with 175 patients per arm, there would be 87% power to detect a 1 day difference in the duration of urinary retention and duration of hospital stay with a 1-sided significance level of 0.05 (this assumes an effect size for this secondary outcome variable of 0.30 [1 day difference in means/pooled standard deviation estimate of 3.33]).

Role in Project:

[name]: Co-Principalinvestigator for the study, responsible for study design, study implementation, data collection, reporting of adverse events, and manuscript preparation.

[name]: Co-investigator responsible for assisting in study implementation, data collection, and manuscript preparation.

[name]: Co-investigator responsible for IRB application, Informed Consent form, and pharmacy liaison.

[name]: Statistician responsible for overseeing statistics performed by the co-PI as part of the CTSA BERD program.

[name]: Member of the Office of Research and Regulatory support who will be assisting with the Investigational New Drug application and corresponding with the FDA.

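### Length of stay is compared without stratifying by procedure; a rank test with two fixed procedure strata would cost almost nothing and might add some power for this secondary outcome

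*Combined protocol and SAP*

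**What the plan says.** All places are in the combined protocol and SAP.

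- **Test for stay (Analysis of the Data):** "An appropriate nonparametric test (e.g. Wilcoxon Rank Sum) will be used for non-normal appearing data as can be anticipated for length of hospital stay". The rank-sum test is given as an example, and no stratum or covariate is attached to it.
- **Power for stay (same section):** "there would be 87% power to detect a 1 day difference in the duration of urinary retention and duration of hospital stay". The plan bases this on a standardised effect of 0.30, described as "1 day difference in means/pooled standard deviation estimate of 3.33", and tests it "with a 1-sided significance level of 0.05". The sample size, set on the primary outcome, is stated thus: "a reasonable estimate for sample size is 175 subjects in both the treatment and control groups".
- **Population (Table 1):** cervical and lumbar laminectomy are pooled with several posterior, interbody and combined fusions.
- **Randomization:** a random numbers table, with no stratification by procedure stated.
- **Data collected (Outcome Measures):** the baseline list includes "length and type of surgery". The listed variables are to be used for adjustment only if the arms differ significantly. Analysis of the Data names the model for this, a multiple linear regression, to be used if needed.
- **Procedure and outcome:** the Abstract, speaking of urinary retention (POUR), gives a figure for simple decompression, "with even higher rates estimated after complex spinal procedures such as instrumented fusion". The Background says that POUR lengthens hospital stay. Subject Recruitment and Retention describes some procedures as ones "that typically have next day hospital discharges and low incidences of POUR", but these are discectomy and foraminotomy, which are excluded.

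**The concern.** If stay differs between laminectomy and fusion, an unstratified rank test leaves that difference in the error term. A stratified test compares patients within procedure class and removes it.

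The conditional regression does not do the same job. Precision comes from using a prognostic factor whether or not it happens to be imbalanced, and the plan uses it only when it is significantly imbalanced. Smaller chance imbalances also go uncorrected. Moreover, the fallback is a linear model for an outcome that the plan itself expects to be non-normal, and its use depends on the data.

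At stake is the power and precision of one secondary comparison. Neither the validity of the test nor the primary outcome is in question.

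**Working it through.** **Inputs from the plan:** 175 per arm, difference 1 day, SD 3.33 days, one-sided 0.05.

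**Assumptions, because the documents give no figures:** half the patients have fusion (f = 0.5); total SD stays at 3.33; mean stay differs by D days between laminectomy alone and fusion.

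**1. The plan's figure.** Noncentrality = (1/3.33) × √(175/2) = 0.3003 × 9.354 = 2.809, with 348 degrees of freedom. One-sided power is 87.7% (noncentral t) or 87.8% (normal), so the stated 87% reproduces. It is a t-test figure. With the rank-sum efficiency of 0.955 under normality it becomes 86.4%.

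**2. Removing variation between procedures.** Within-class SD = √(3.33² − f(1 − f)D²), and the share of variance removed = f(1 − f)D²/3.33². For D = 2: √(11.089 − 1.000) = 3.18, share 0.09, noncentrality (1/3.18) × 9.354 ≈ 2.945, power 90.2%.

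| Assumed gap D (days) | Share removed | Within-class SD | Power (t) | N per arm for the unstratified power |
|---|---|---|---|---|
| 0 | 0 | 3.33 | 87.7% | 175 |
| 1 | 0.02 | 3.29 | 88.3% | 172 |
| 2 | 0.09 | 3.18 | 90.2% | 160 |
| 3 | 0.20 | 2.97 | 93.3% | 140 |

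With 30% or 70% fusion, the normal formula gives 88.3%, 89.9% and 92.5% for gaps of 1, 2 and 3 days.

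**3. The rank tests themselves.** Simulation with 4,000 runs per setting, 350 patients and a 1-day effect; rank sum against van Elteren:

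| D (days) | Normal data | Skewed whole-day stays (lognormal, assumed mean about 5 days) |
|---|---|---|
| 0 | 86.0% vs 85.7% | 95.3% vs 95.3% |
| 1 | 86.7% vs 87.4% | 95.1% vs 95.2% |
| 2 | 87.4% vs 89.6% | 94.7% vs 96.2% |
| 3 | 86.1% vs 92.6% | 93.8% vs 98.0% |

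With no treatment effect (2,000 runs per setting, gaps 0 to 4), both tests rejected in about 4% to 6% of runs. Both are valid, and stratifying loses nothing material when there is no gap.

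**4. Smaller treatment effects.** The 1-day effect is demanding. If tamsulosin shortens stay only by preventing POUR, the plan's fall from 20% to 10% means that each prevented case must save 1/0.10 = 10 days. If a prevented case saves 2 to 3 days (assumption), the mean shift is 0.2 to 0.3 day. Power by the formula in step 2:

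| True effect (days) | Unstratified | D = 2 | D = 3 |
|---|---|---|---|
| 0.5 | 40.4% | 43% | 47.0% |
| 0.3 | 21.1% | 22.3% | 24.1% |
| 0.2 | 13.9% | 14.5% | 15.5% |

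**5. What the imbalance trigger leaves.** The standard error of the difference in fusion share is √(2 × 0.25/175) = 0.053, so the 95% range is ±10.5 percentage points. A 5% baseline test triggers at about the same point. An imbalance just short of it moves the difference in mean stay by 0.105 × 2 = 0.21 day or 0.105 × 3 = 0.31 day for gaps of 2 or 3 days.

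**The case against.** The strongest objection is that nothing in the documents shows a difference in stay between eligible laminectomy and eligible fusion. A reader might take the next-day-discharge remark as the plan's own statement that stay depends on procedure within the trial. It is not: it describes excluded procedures, and excluding them already narrows the range of stays. The link for eligible patients is indirect: more POUR after fusion, and longer stay with POUR. This objection stands, and it is why the gain cannot be sized from the documents.

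Second, the plan is not silent. Type of surgery is on the adjustment list, and the rank-sum test is only an example. So it would be wrong to say that imbalance in procedure is left uncontrolled. What remains is that adjustment after a significant imbalance does not secure precision.

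Third, a reader might infer that the unstratified test is biased or invalid. Randomisation is not stratified and the type I error holds, so that inference fails.

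Fourth, a reader might extend the point to the primary outcome. With assumed control rates of 12% and 28%, both halved by treatment, a Cochran-Mantel-Haenszel test raised simulated power only from 84% to 85%. That does not justify replacing the test on which the sample size was built.

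Finally, the gain is small when power is already high, and it does not rescue a comparison whose true effect is 0.2 to 0.3 day. That also stands.

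**Conclusion.** The point holds as a cheap improvement to a secondary analysis. Stay is compared without stratification across laminectomy and fusion, and the conditional regression does not supply the missing precision. The gain is 0.6, 2.5 or 5.6 percentage points (87.7% to 88.3%, 90.2% or 93.3%) for an assumed gap of 1, 2 or 3 days, and nil with no gap. This rests on half the patients having fusion, total SD 3.33 and a 1-day effect. At a 0.5-day effect the gain for gaps of 2 and 3 days is of similar size. At 0.2 to 0.3 day it shrinks to between 0.6 and 3 points. The planned test remains valid, and the documents do not show that any particular amount of power is being lost.

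**What to change.** Prespecify in Analysis of the Data that length of stay will be compared by a van Elteren test with two fixed strata, laminectomy alone and any fusion. Define the stratum by the procedure planned at consent, so that it precedes randomisation, and use it whatever baseline balance is observed. Add no further strata that depend on the numbers seen, and leave the primary POUR test unchanged. Make the change before the unblinded interim analysis planned once 75 or more patients have completed.

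The cost is one sentence in the plan and one field at consent. That field is needed because the plan lists type of surgery as collected but does not list the planned procedure class as a separate item. No patients, visits or procedures are added.
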